Discussion: This study will determine whether intranasal ketamine is an effective alternative to intranasal fentanyl for analgesia in children. This would be particularly useful in children who experience adverse effects with opioids, have developed opioid tolerance as a result of chronic painful conditions, have poor opioid sensitivity due to their genetic predisposition, in pediatric trauma patients with hypotension or in patients requiring procedural sedation during their emergency department visit.

II. PURPOSE OF STUDY

The purpose of this study is to compare intranasal sub-dissociative dosing of ketamine with intranasal fentanyl for acute pain associated with traumatic limb injuries in children 8-17 years of age presenting to the emergency department.

Primary Objective (or Aim)

The primary objective of this study is to determine if intranasal sub-dissociative ketamine (1.5 mg/kg) is non-inferior to intranasal fentanyl (2 mcg/kg) in reduction of moderate and severe pain (VAS score greater than 35 mm [1]) associated with extremity injuries in children ages 8 years through 17 years of age.

Hypothesis #1: Intranasal sub-dissociative ketamine (1.5 mg/kg) and intranasal fentanyl (2 mcg/kg) will both reduce pain by a mean VAS score of at least 15 mm. There will be no significant difference in the means for reduction in pain score between patients receiving intranasal ketamine and those receiving intranasal fentanyl.

Secondary Objective (or Aim)

The secondary objective is to define and compare the level of sedation associated with intranasal sub-dissociative ketamine (1.5 mg/kg) and intranasal fentanyl (2 mcg/kg) as measured by the University of Michigan Sedation Scale Score and capnometry values.

Hypothesis #2a: There will be no significant difference in mean sedation scale scores between the intranasal ketamine group and the intranasal fentanyl group.

Hypothesis #2b: There will be no significant difference in the mean capnometry values of the two groups. Patients in both groups will not experience hypopneic hypoventilation (decrease in capnometry value of ≥ 10 mm Hg).

III. BACKGROUND

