The sample size calculation is based on a non-inferiority test of the difference between two means. Group sample sizes of 39 and 39 achieve 80% power to detect non-inferiority using a one-sided, two-sample t-test. The margin of non-inferiority is 10. Literature has shown that the minimum clinically significant difference in VAS pain score in children is 10-12 [65, 66] which is why 10 was chosen as our non-inferiority margin. The true difference between the means is assumed to be 5 based on the PICHFORK trial, which found a median rating reduction of 40 mm (IQR 20 to 45) at 30 minutes for fentanyl and a median rating reduction of 45 mm (IQR 20-60) at 30 minutes for ketamine, and therefore, a difference in medians of 5 (-10 to 20, 95% CI) [60]. Using the IQR information from the PICHFORK trial and assuming normality for the pain scores, we estimate the standard deviations to be 29.63 and 22.22 for the rating reduction at 30 minutes for the fentanyl and ketamine groups, respectively. Therefore, with an α of 0.05 and a β of 0.2 (80% power), the sample size required to detect this difference was estimated to be 39 subjects in each group, for a total of 78 subjects. In order to achieve this number of evaluable subjects, we plan to enroll 90 subjects, anticipating that not all subjects enrolled will be fully evaluable. Over the last year, there were 634 patients who presented to the CCHMC ED and were triaged as orthopedic evaluations. Of these, 360 were in the age group specified in the inclusion criteria. Given this data, we expect to be able to successfully complete this study as planned.

VII. STUDY PROCEDURES

Table 4. Study Procedures

Visits	Visit 1						Visit 2
	Screening Phase	Enrollment	15 (±5) min	30 (±5) min	60 (±5) min	120 (+30) min	+30 (±5) days *
Informed Consent, Assent for subjects ages 12-17		X					
Review Inclusion/Exclusion Criteria	X						
Demographics/Medical History	X						
Physical Examination	X						
Vital signs (HR, RR, BP, O2 sat)		X	X	X	X	X	
Serum or urine pregnancy test for postmenarchal females	X						
Weight	X						
VAS pain score		X	X	X	X		
UMSS sedation score		X	X	X	X		
Nasal mucosal exam	X					X	
Smell test	X					X	
Capnometry value		X	X	X	X		
Randomization		X					
Dispense study drug		X					
Adverse event/Serious adverse event assessment		X	X	X	X	X	X

*Visit 2 window +/- 5 days.

(See Appendix C for study flow diagram, Appendix D for current orthopedic evaluation flow diagram, and Appendix E for duration of study procedures)

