Additionally, data about missed eligible patients will be collected periodically through an EMR report and supplemented by chart review to assess screening hours, training needs or other issues that may inhibit staff's ability to enroll. We are requesting a HIPAA waiver to review the patient charts via the MRN and day/time of arrival and no information will be used for analysis in the research study. Consent would not otherwise be possible for these participants because of the nature of presentation to the ED; it is possible that these patients will have arrived when no study staff is available. Data collected on missed eligible patients will include MRN, encounter ID, date/time of ED arrival and discharge, means of arrival, date of birth, gender, whether or not they met study inclusion/exclusion criteria, disposition, discharge diagnosis, and provider name.

Primary Endpoint

The primary endpoint is the difference between the mean reduction in pain scores between the ketamine group and the fentanyl group as measured by the visual analog scale (VAS) at 30 minutes after study intervention.

The pain VAS is a unidimensional measure of pain intensity which has been widely used in diverse populations [66, 72, 73]. It is a continuous scale comprised of a horizontal or vertical line that is 10 cm (100 mm) in length anchored by two verbal descriptors representing pain extremes. The scale is most

commonly anchored by “no pain” (score of 0) and “pain as bad as it could be” or “worst imaginable pain” (score of 100). To avoid clustering of scores around a preferred numeric value, numbers or verbal descriptors at intermediate points are not present. The patient is asked to place a line perpendicular to the VAS line at the point that represents their current pain intensity. Using a ruler, the score is determined by measuring the distance (mm) on the 10-cm line between the “no pain” anchor and the patient's mark, providing a range of scores from 0–100. The visual analog scale has been shown to be valid and reliable in children 8 to 17 years of age suffering from acute pain and that a minimum clinically significant difference in VAS score ranges from 10 to 12 mm in children and adolescents [65, 66]. The optimal cut points for mild, moderate and severe pain on the VAS for children and adolescents have been determined to be 35 and 60 mm [1].

Secondary Endpoints

The secondary endpoints are to:

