University of Michigan Sedation Scale (UMSS) scores will also be obtained at baseline, 15, 30 and 60 minutes after study intervention. The University of Michigan Sedation Scale is a valid and reliable tool that allows for rapid assessment of the depth of sedation in children. It is a simple observational tool that assesses the level of alertness on a five-point scale [74]. It has been validated in children and has shown to have significant inter-rater reliability.

UMSS	Clinical Features
0	Awake and alert
1	Minimally sedated; tired/sleepy, appropriate response to verbal conversation and/or sound
2	Moderately sedated; somnolent/sleeping, easily aroused with light tactile stimulation or a simple verbal command
3	Deeply sedated; deep sleep, arousable only with significant physical stimulation
4	Unarousable

UMSS = University of Michigan Sedation Scale.

Efficacy Evaluations

Diagnostic Tests, Scales, Measures

A VAS score, UMSS sedation score and vital signs will be obtained at study entry and at 15 minutes, 30 minutes and 60 minutes after administration of study medication. Changes between these time points will be evaluated. The time from initial physician evaluation to study medication and to ED disposition will be recorded. Adjunct measures including additional analgesia or anti-emetics will be recorded.

Of note, pain scores, sedation scores, vital signs, capnometry values, and adverse effects will be obtained at specific windows of time such that the “15 minute” value will be obtained between 10 and 20 minutes after medication is given, “30 minute” value will be obtained between 25 and 35 minutes after medication is given, “60 minute” value will be obtained between 55 and 65 minutes after medication is given and “120 minute” value will be obtained between 120 and 150 minutes after medication is given.

Statistical Methods

Baseline Data

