Baseline and demographic characteristics will be summarized by standard descriptive summary statistics. This will include means and standard deviations for continuous variables expected to be normally distributed, such as age, vital signs, capnometry values, weight and VAS pain scores; proportions for categorical variables such as gender, race and injury location; and medians with ranges for variables expected to not be normally distributed, such as UMSS sedation scores. All continuous variables will be assessed for normality; parametric statistics will be used for normally distributed variables and non-parametric statistics will be used for non-normally distributed variables.

Efficacy Analysis

The primary analysis will include all subjects randomized based on the principle of intention to treat. If necessary, a per-protocol analysis will also be performed to assess efficacy of the treatments actually received. The primary efficacy endpoint will be the difference in mean pain scores between the ketamine group and the fentanyl group at 30 minutes after study intervention. This difference will be evaluated using the t-test.

Demographic and historical baseline information of the 2 study groups will be compared using t-tests (means), Mann-Whitney U (medians), and chi-square (proportions) tests. If there are any significant differences, linear regression will be performed to adjust for significantly different covariates.

For secondary outcomes, t-tests, or Mann-Whitney U where appropriate, will be used to evaluate differences in continuous outcomes (e.g. heart rate, blood pressure). Chi-square tests will be used to evaluate proportions in dichotomous outcomes (e.g. proportion with presence of specific adverse effects). Risk differences with 95% confidence intervals will be used to compare dichotomous outcomes such as the use of rescue analgesia and adverse events.

Safety Analysis

All subjects entered into the study will be included in the safety analysis. The frequencies of adverse events, including type, body system, severity and relationship to the study drug, will be summarized. We do not anticipate any serious adverse events. However, if one were to occur, it would be described in detail.

Adverse event incidence will be summarized along with the corresponding exact binomial 95% two-sided confidence intervals.

Test of Non-Inferiority

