A one-sided two-sample t-test will be used to test whether the pain reduction using ketamine is non-inferior to that of fentanyl. When the variances of the two groups are unequal, Welch's t-test will be used; if the data are not normally distributed, the Mann-Whitney (Wilcoxon signed rank) U test will be used [75, 76].

Interim Analysis

Due to the expected short duration of the study, no interim analysis will be performed. However, ongoing safety analysis of adverse events, serious adverse events and toxicities will be done.

IX. FACILITIES AND PERFORMANCE SITES

The study will be conducted at one investigative site in the United States. Cincinnati Children's Hospital Medical Center is an academic, freestanding, 523 bed children's hospital with 32,981 admissions and 125,130 Emergency Department visits annually. The population is diverse and includes 51% Caucasian, 40% African American, 2% Hispanic, and 7% other. Study enrollment will only be performed at the base campus.

X. POTENTIAL BENEFITS

Intranasal sub-dissociative dosing of ketamine has been shown in multiple studies to provide adequate analgesia to pediatric patients experiencing moderate to severe pain. Therefore, patients receiving the study medication may receive adequate analgesia and avoid the side effects associated with opioids and potentially the increased chance of adverse effects as a result of opioids in combination with ketamine procedural sedation later during their ED visit. Furthermore, patients who are genetically predisposed to have poor opioid sensitivity or those who have developed opioid tolerance due to other chronic painful conditions may find more benefit with the study medication.

XI. POTENTIAL RISKS, DISCOMFORTS, INCONVENIENCES and PRECAUTIONS

There are minimal risks associated with the administration of sub-dissociative ketamine via the intranasal route. All studies performed using intranasal ketamine at sub-dissociative dosing in children showed only minimal adverse events and no serious adverse events associated with the study medication. Examples of mild adverse events which could be expected to occur with both medications include drowsiness,

dizziness, pruritus, nausea, vomiting, dysphoria, unpleasant taste, vision changes, throat irritation, headache, and mild increase in heart rate and blood pressure.

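### Covariate adjustment is chosen by baseline significance tests, baseline VAS is not pre-specified, and the plan does not say whether the adjusted or the unadjusted result decides non-inferiority

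*Combined protocol and SAP*

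**What the plan says.** Efficacy Analysis (Section VIII, Statistical Methods) does three things.

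- It states the primary variable: "The primary efficacy endpoint will be the difference in mean pain scores between the ketamine group and the fentanyl group at 30 minutes". A t-test is named, with no margin or sidedness given there.
- It compares demographic and historical baseline data between arms with t-tests, Mann-Whitney tests and chi-square tests.
- If any differ significantly, it adjusts for those covariates by linear regression. It gives no level for the baseline tests and no cross-reference to Table 5.

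Test of Non-Inferiority then says: "A one-sided two-sample t-test will be used to test whether the pain reduction using ketamine is non-inferior to that of fentanyl". Welch's test covers unequal variances, and "if the data are not normally distributed, the Mann-Whitney (Wilcoxon signed rank) U test will be used". The regression is not mentioned.

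Table 5 lists ten covariates, and baseline VAS is not among them. Table 4 schedules a VAS score at enrollment, and Baseline Data lists VAS among the variables to be summarized.

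On the variable itself, the Primary Endpoint section reads "The primary endpoint is the difference between the mean reduction in pain scores between the ketamine group and the fentanyl group". Hypothesis #1 reads "There will be no significant difference in the means for reduction in pain score between patients receiving intranasal ketamine". The sample size section says "we estimate the standard deviations to be 29.63 and 22.22 for the rating reduction at 30 minutes". Efficacy Evaluations adds, of the scores at the successive time points, "Changes between these time points will be evaluated". Secondary Endpoints words the 15- and 60-minute comparison as pain score.

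**The concern.** In a randomized trial, baseline differences between arms arise by chance. A rule that adjusts only for what happens to reach significance therefore lets chance choose the model. It also does not look for covariates that predict outcome. The one that is arithmetically part of the outcome, baseline VAS, enters only if it is among the variables tested and happens to be imbalanced.

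When the rule fires, the trial has an unadjusted result from Test of Non-Inferiority and an adjusted result from Efficacy Analysis. Nothing says which is compared with the 10 mm margin. What is at stake is precision, and a choice of primary result that could be made after both are known.

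The sentence naming the score rather than the reduction is a separate and smaller matter of wording.

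**Working it through.** **Inputs from the plan (Sample Size and Power Analysis).** 39 per arm; margin 10 mm; one-sided alpha 0.05; true difference 5 mm, taken in ketamine's favor; SDs of the reduction 29.63 (fentanyl) and 22.22 (ketamine).

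**Assumed, not in the documents.** Baseline VAS SD (sb) 15–20 mm; correlation of baseline with 30-minute VAS (r) 0.2–0.6; normal data.

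**1. The plan's figure.** Root mean square SD = √[(29.63² + 22.22²)/2] = 26.19. By normal approximation, n = 2 × 26.19² × (1.645 + 0.842)² / (10 + 5)² = 37.7, so 38 per arm. With the t distribution it is 39, with power 0.805. The stated 39 reproduces, and it rests on SDs of the reduction.

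One caveat: these SDs do not match the quoted quartiles, "which found a median rating reduction of 40 mm (IQR 20 to 45) at 30 minutes for fentanyl" and 20–60 for ketamine. Dividing the widths by 1.35 gives 25/1.35 = 18.52 for fentanyl and 40/1.35 = 29.63 for ketamine. That is a separate sample-size question, and the stated SDs are used here at face value.

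**2. Adjusting for baseline VAS.** Each arm's 30-minute SD (sp) solves sp² − 2·r·sb·sp + sb² = SD². After adjustment the residual SD is about sp·√(1 − r²).

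- Example, sb = 20 and r = 0.2: sp = 14.5 (ketamine) and 26.2 (fentanyl); residual SDs 14.2 and 25.7.
- SE = √[(14.2² + 25.7²)/39] = 4.70, against √[(22.22² + 29.63²)/39] = 5.93 unadjusted.
- Simulation of ten scenarios (sb 15 or 20; r 0.2 to 0.6 in steps of 0.1; 20,000 trials each), with HC2 robust standard errors for the adjusted model:

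| | Adjusted | Unadjusted Welch |
|---|---|---|
| Power at +5 mm | 0.80–0.93 | 0.80–0.81 |
| Type I error at −10 mm | 0.046–0.053 | 0.048–0.053 |

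The gain disappears where the slope of 30-minute on baseline VAS (r·sp/sb) is close to 1, which here means the higher correlations.

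**3. How often the rule fires by chance.** Assume the Table 5 covariates are tested at 5%. Ten independent tests give 1 − 0.95¹⁰ = 0.40; five effective tests give 1 − 0.95⁵ = 0.23. Several items are plausibly related (age with weight, the two times to medication, the injury descriptors), so 40% is an upper figure.

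**4. How often firing changes the verdict.** Assume independent covariates that jointly explain 0–30% of the variance of the reduction.

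| Share of all trials with a changed verdict | True +5 mm | Equality |
|---|---|---|
| Five tests | 1.7–4.0% | 2.5–4.9% |
| Ten tests | 3.0–5.3% | 3.5–7.2% |

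Type I error with the rule followed strictly is 0.043–0.052.

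**5. Free choice between two results.** If success could be claimed on either the unadjusted or the baseline-VAS-adjusted result, type I error is roughly 5.5–7.5%. This supposes that both results are always available, so it illustrates an open choice and is not a property of the written rule.

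**6. The score wording, if followed literally.** Three of the ten scenarios imply a slope above 1 in at least one arm: sb 15 with r 0.5, sb 15 with r 0.6, and sb 20 with r 0.6 (fentanyl 0.6 × 36.9/20 = 1.11). Setting these aside, score and reduction give opposite verdicts in about 12–19% of trials at +5 mm and 18–29% at equality. With VAS bounded at 0–100 and baseline at least 35, the figures are 11–16% and 18–24%.

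**The case against.** The strongest reply is that the plan already contains a valid primary analysis. Test of Non-Inferiority names the reduction, matches the variable on which the trial was powered, and keeps its 5% error. The reduction already uses baseline VAS, so leaving it out as a covariate is not an error, and the gain from adding it may be nil. Table 5 is titled Covariates and is the natural set for the baseline tests. The rule changes few verdicts.

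All of that stands, and it limits the point. It does not settle which result decides once the regression is triggered, because neither section mentions the other's analysis.

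Two stronger readings are tempting.

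- A reader might infer from the Efficacy Analysis sentence that the primary variable is undecided, or that the trial would test the wrong one. The documents do not support this. Hypothesis #1, the sample size, the Primary Endpoint section and the non-inferiority test all use the reduction. The disagreement rates in step 6 describe an analysis that the non-inferiority section does not run.
- A reader might infer that the covariate rule biases the trial or inflates its error. Followed strictly, it does neither in these calculations.

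**Conclusion.** The point holds as a gap in specification with a nearly free improvement attached. Significance-triggered adjustment leaves two candidate primary results with no stated order, and the covariate most directly tied to the outcome is not pre-specified.

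Its size is modest: a power gain from nil to about 0.12 for adjusting on baseline VAS, and a changed verdict in about 2–7% of all trials from the rule itself. The power figures rest on the stated SDs and an assumed baseline SD and correlation. The rule figures rest on an assumed test level, covariate set and explained variance. The absence of a stated deciding analysis rests on the text alone.

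The pain-score wording is minor and needs only correction. The change should be made, but the plan is not invalid without it.

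**What to change.** 1. In Efficacy Analysis, replace the significance-triggered rule with one primary model and cross-reference it in Test of Non-Inferiority: linear regression of the 30-minute VAS reduction on arm and baseline VAS, with HC2 heteroscedasticity-robust standard errors. Non-inferiority is shown if the lower one-sided 95% confidence limit for ketamine minus fentanyl reduction lies above −10 mm. Keep the unadjusted test on the reduction as a named sensitivity analysis that does not decide.
2. Minimum alternative, if no covariate is wanted: state that the existing test on the reduction is the sole decision and that any regression is supportive.
3. Report baseline comparisons descriptively, and add baseline VAS to Table 5.
4. In Efficacy Analysis, name the mean reduction in VAS at 30 minutes as the primary variable, and align the 15- and 60-minute wording in Secondary Endpoints.

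The cost is SAP wording and one degree of freedom. Baseline VAS is already collected, and sample size and procedures do not change. If the correlation is high, the adjusted model brings no power gain, but the simulated loss is no more than 0.005, within simulation error.

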- Define and compare the level of sedation associated with intranasal sub-dissociative ketamine (1.5 mg/kg) and intranasal fentanyl (2 mcg/kg) as measured by the University of Michigan Sedation Scale Score and capnometry values.
- Compare adverse effects associated with intranasal sub-dissociative ketamine and intranasal fentanyl
- Compare vital sign changes associated with intranasal sub-dissociative ketamine and intranasal fentanyl

An additional secondary endpoint will be the difference between the ketamine group and the fentanyl group in pain score as measured by the visual analog scale at 15 and 60 minutes after study intervention.

Screening and Baseline Evaluation

Physical Examination

Baseline evaluation will include a physical examination and demographics as are routinely performed during the orthopedic evaluation process. Items recorded from physical examination will be weight and extremity injured. An exam of the nasal mucosa will be performed, and a nasal smell test will be administered prior to drug treatment and at 120 minutes post treatment. Demographic data recorded will include age, gender, ethnicity and race.

If there is a discrepancy between the information provided by the parent and information provided in the chart, the information provided by the parent will be used.

Vital signs

Vital sign data will be recorded at baseline, 15 minutes, 30 minutes, 60 minutes, and 120 minutes. It will include heart rate, respiratory rate, blood pressure, oxygen saturation and end tidal capnometry value. However, an end tidal capnometry value will not be obtained at the 120 minute assessment. Oxygen saturation levels and capnometry values will be obtained from the cardio-respiratory monitor once an appropriate waveform is obtained. Cardio-respiratory monitoring with pulse oximetry will be continuous for 120 minutes after the study medication is administered.

Table 5. Covariates

Age
Gender
Race
Insurance status
Weight
Time to medication from injury
Time to medication from arrival to ED
Injury Type
Extremity injured
Mechanism of injury

Other Evaluations/Measures

A urine or serum pregnancy test will be collected from all post menarchal females, and results must be negative before drug treatment may be initiated.

Visual analog scale pain scores will be obtained by study staff as described above.

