Based on pharmacokinetic studies on intranasal ketamine use in children, the mean plasma concentrations peaked at about 20 minutes and the plasma concentrations of norketamine (the predominate active metabolite), peaked at about 120 minutes after administration of intranasal ketamine. Subjects will be observed in the emergency department for a minimum of 2 hours after study medication administration, thus providing resources and personnel for immediate, emergency care should the need arise. Those patients who are admitted and remain in the ED less than 2 hours will be monitored for the entirety of their ED stay. The admitting team will then be notified that they received a study medication. This length of observation is consistent with the amount of time that patients who are triaged as an orthopedic evaluation spend in the ED for standard therapy as most of these patients tend to remain in the ED for longer than two hours. This observation time does not pose any increased risk to the patient. Those patients discharged from the ED will be provided appropriate follow up instructions as per standard of care.

For these reasons, we expect enrollment in this trial to be of minimal risk to patients.

XII. RISK/BENEFIT ANALYSIS

Due to the prospect of direct benefit to patients and minimal risk to patients, the risk-benefit ratio seems favorable to patients, parents and providers.

XIII. DATA AND SAFETY MONITORING

Clinical Adverse Events

Clinical adverse events (AEs) will be monitored throughout the study. All adverse events will be followed until resolution.

Adverse Event Reporting

All on-site serious adverse events will be reported to the IRB in accordance with CCHMC IRB policies. Adverse Events will be reported to the IRB per CCHMC Research Policy R-18.

Definition of an Adverse Event

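### Vital signs would be compared more precisely by regression on each child's own baseline, applied unconditionally and with 95% intervals, than by t-test or Mann-Whitney alone

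*Combined protocol and SAP*

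**What the plan says.** In Section VIII, Secondary Endpoints, one aim reads "Compare vital sign changes associated with intranasal sub-dissociative ketamine and intranasal fentanyl". The Vital signs subsection says "Vital sign data will be recorded at baseline, 15 minutes, 30 minutes, 60 minutes, and 120 minutes". It counts end-tidal capnometry among the vital signs, except at 120 minutes.

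Under Diagnostic Tests, Scales, Measures, the plan lists pain score, sedation score and vital signs together at entry, 15, 30 and 60 minutes, and adds "Changes between these time points will be evaluated". The next paragraph gives a window for a 120-minute value.

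For continuous secondary outcomes the Efficacy Analysis says only that "t-tests, or Mann-Whitney U where appropriate, will be used to evaluate differences in continuous outcomes (e.g. heart rate, blood pressure" being the examples. It does not say whether the post-dose value or the change is tested, and it states no interval. For dichotomous outcomes it does: "Risk differences with 95% confidence intervals will be used to compare dichotomous outcomes such as the use of rescue analgesia and adverse events".

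The one regression is conditional. "Demographic and historical baseline information of the 2 study groups will be compared using t-tests (means", with other tests for medians and proportions, and then "If there are any significant differences, linear regression will be performed to adjust for significantly different covariates". No outcome is named for that regression. Table 5 lists ten covariates, none of them a vital sign, although the Baseline Data paragraph does include vital signs among the baseline variables to be summarised.

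**The concern.** Each child's heart rate, respiratory rate, blood pressure and end-tidal CO2 before dosing are measured and are likely to predict the later reading. The plan does not commit to using them as model terms. A baseline vital sign could enter the conditional regression only if it were treated as demographic or historical information and also differed significantly between arms. A moderate chance imbalance would not meet that second condition.

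At stake is the precision, and the form of reporting, of the between-arm statement on vital signs: a p-value from an unadjusted test rather than an adjusted difference with an interval.

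**Working it through.** **The plan's own figure.** The documents give no precision or power figure for vital signs, so the only stated figure to reproduce is the 39 per arm for the primary test. Pooled SD = √((29.63² + 22.22²)/2) = 26.19. With margin 10 and ketamine assumed 5 mm better, the distance is 15. The normal approximation gives 2 × (1.645 + 0.842)² × 26.19²/15² = 37.7, so 38. The noncentral t gives 39 (power 80.6%). The figure reproduces and does not depend on the present point. It is used below only as the number per arm.

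**Inputs.**
- n = 39 per arm, from Sample Size and Power Analysis in Section VI.
- Correlation ρ between baseline and post-dose value: not in the documents, assumed 0.5 to 0.8.
- Results are in units of the vital sign's SD, taken as equal at baseline and follow-up. No SD is given either.

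**Variance of the arm difference, relative to the raw value.**
- Post-dose value only: 1
- Change from baseline: 2(1 − ρ)
- Adjusted for baseline: 1 − ρ²
- Adjusted against change: (1 − ρ²)/(2(1 − ρ)) = (1 + ρ)/2

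**95% interval half-width** = t × √(2/39) × √(relative variance). Here √(2/39) = 0.226 and t = 1.992 (76 df for change, 75 for adjusted).

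| ρ | Relative variance, change | Relative variance, adjusted | Half-width, change (SD) | Half-width, adjusted (SD) | Narrower by |
|---|---|---|---|---|---|
| 0.5 | 1.00 | 0.75 | 0.451 | 0.391 | 13% |
| 0.7 | 0.60 | 0.51 | 0.349 | 0.322 | 8% |
| 0.8 | 0.40 | 0.36 | 0.285 | 0.271 | 5% |

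The proportional gain is essentially the same at 45 per arm (all 90 enrolled), because the ratio √((1 + ρ)/2) does not involve n.

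**If the post-dose value alone were tested.** The Efficacy Analysis wording allows this reading. The half-width is then 0.451 SD at every ρ, and adjustment narrows it by 13%, 29% and 40% at ρ = 0.5, 0.7 and 0.8 (0.391, 0.322 and 0.271 against 0.451). The endpoint wording favours change, so the table above is the fairer comparison.

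**Why the conditional rule does not fill the gap.** Take a chance baseline difference of 0.3 SD. Its standard error is 0.226, so z = 0.3/0.226 = 1.32 and p is about 0.19: no adjustment is triggered. The change-score estimate shifts by (1 − ρ) × 0.3, which is 0.15, 0.09 or 0.06 SD at ρ = 0.5, 0.7 or 0.8. Over repeated randomisations this averages to zero. It is imprecision, not bias.

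**The case against.** The strongest reply is that this is a preference between valid methods. The endpoint is defined as change and the plan says changes will be evaluated, so baseline is already used, by subtraction. The Baseline Data paragraph names vital signs, so a conditional route into the regression is arguable. The plan sets no power target for vital signs, and both the SD and ρ here are assumptions. Most of this stands. It limits the point to a modest gain in precision and a missing interval.

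Four stronger readings are tempting, and the documents do not support them.

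- *Baseline is ignored or the test is biased.* It enters by subtraction if change is tested, and a two-sample test is valid under randomisation either way.
- *The 120-minute reading will not be compared.* The sentence that stops at 60 minutes lists vital signs with pain and sedation scores, which Table 4 does not schedule at 120 minutes, so the stop looks like drafting. The endpoint and the named test carry no time limit. Section XI does say "the plasma concentrations of norketamine (the predominate active metabolite), peaked at about 120 minutes after administration of intranasal ketamine", but it says this alongside the two-hour observation period and claims no haemodynamic effect; it puts the peak of ketamine itself at about 20 minutes.
- *Harm could be missed.* Section XI lists mild rises in heart rate and blood pressure as expected adverse events, Section XIII has all identified events recorded, and the Efficacy Analysis compares adverse events by arm with risk differences and 95% intervals. Section VII also has a study physician judge out-of-range vital signs.
- *The trial loses substantial power.* A power contrast can be computed for an assumed effect, but the remedy reports estimates with intervals, so interval width is the relevant measure.

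**Conclusion.** The point holds as a minor, nearly free improvement. The planned comparison of vital signs is valid but uses the collected baseline less efficiently than it could, and it states no interval. Against a change-score test at 39 per arm, unconditional baseline adjustment narrows the 95% interval by about 13% at ρ = 0.5, 8% at 0.7 and 5% at 0.8.

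This rests on an assumed correlation, equal SDs at baseline and follow-up, and the reading that change is what would be tested. The primary non-inferiority conclusion, the sample size and the capture of serious harm do not change.

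**What to change.** In the secondary-outcome paragraph of the Efficacy Analysis, add:

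> Heart rate, respiratory rate, systolic and diastolic pressure and end-tidal CO2 at 15, 30 and 60 minutes (and all but end-tidal CO2 at 120 minutes) will be compared by linear regression of the post-dose value on arm and the child's own baseline value, whether or not baseline differs, and adjusted differences will be reported with 95% CIs. Where the residuals are clearly non-normal (for example oxygen saturation, if skewed), Mann-Whitney on change from baseline will be used.

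End-tidal CO2 belongs here because the plan counts it as a vital sign and Hypothesis 2b concerns it. The second sentence keeps the plan's non-parametric fallback. The 120-minute comparison should be called descriptive: children admitted early may leave before it (Section XI), and rescue analgesia may have been given by then (Section VII). Adding 120 minutes to the sentence on changes under Diagnostic Tests, Scales, Measures is a clarification only.

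The cost is a few lines of text and one degree of freedom per model, with no new data. Four measures at four times plus end-tidal CO2 at three makes 4 × 4 + 3 = 19 comparisons. If each were tested at 5% with no true differences, about 19 × 0.05 = 0.95 false positives would be expected, so the results should be read as estimates with intervals, not as a set of significance tests.
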